11.6.2 Laboratory Evaluations

Summary statistics for baseline and change from baseline during the protocol specified treatment phase of the investigation will be summarized for both treatment groups for all hematology and chemistry parameters, including liver function tests and electrolytes, as well as alpha-fetoprotein. Urinalysis data will be presented in the data listings only.

11.6.3 Vital Signs

Summary statistics for baseline and change from baseline during the protocol specified treatment phase of the investigation will be summarized for both treatment groups for the following vital sign parameters:

- Blood pressure (mmHg)
- Pulse (beats per minute)
- Respiration rate (breaths per minute)
- Temperature (°C)

11.6.4 Physical Examinations

Data from physical exams (scheduled and unscheduled) during the protocol specified treatment phase will be presented in the data listings. All pre-treatment clinically significant findings, as determined by the Investigator, will be reported as concurrent medical conditions. All clinically

significant findings on exams performed after treatment initiation will be reported as adverse events.

11.6.5 Eastern Cooperative Oncology Group (ECOG) Performance Status

ECOG data will be collected at baseline and the final study visit and will be presented in the data listings. A summary table will be created summarizing the ECOG results as the number and percent of patients in each ECOG category for each treatment group for both timepoints.

11.6.6 Electrocardiogram (ECG)

Electrocardiograms will be performed at baseline and the final study visit. Investigators will interpret the results and classify each ECG as follows:

- Normal
- Abnormal, not clinically significant
- Abnormal, clinically significant

For all abnormal findings, the investigator will provide a brief description of the abnormality. All clinically significant abnormal findings found at the final study visit which were not present at baseline will be reported as adverse events. A summary table will be generated summarizing the ECG results for baseline and final study visit as classified by the PI as the number and percent of patients in each category for each treatment group. All ECG data will be reported in the data listings.

11.6.7 Cardiac Ejection Fraction (%)

Cardiac ejection fraction data will be collected at screening, after the second TACE, and at the final study visit for all patients. Cardiac ejection fraction testing will also be collected at additional time points during the protocol specified treatment phase of the investigation if the patient has experienced a cardiac related adverse event. Abnormal findings will be reported as adverse events. A summary table will be created summarizing the number and percent of patients having a clinically significant cardiac ejection fraction finding at each time point for each treatment group. This data will be presented in the data listings.

12 Data Safety Monitoring Board

A Data Safety Monitoring Board will be formed consisting of at least 3 individuals with expertise and experience in clinical trials, liver cancer and safety evaluations, but without direct involvement in the conduct of the study. The exact responsibilities, procedures, and guidelines used to manage the DSMB are described in a separate charter.

13 Records and Confidentiality

Each patient will be identified by study number only in the trial records. Study data will be recorded on pre-printed CRFs. Monitoring of study data recorded on the CRFs to source documents will be conducted for all patients to ensure accuracy and completeness.

14 Quality Control and Assurance

This study will be initiated and conducted under the sponsorship of BioSphere Medical, Inc., a wholly owned subsidiary of Merit Medical Inc. BioSphere Medical will supply pre-printed CRFs to all sites. Representatives of BioSphere Medical will monitor the study to verify study data, medical records, and CRF data in accordance with current ICH, GCPs and other applicable regulations and guidelines.

15 Good Clinical Practice

The study will be conducted in accordance with the International Conference on Harmonization (ICH) E6 for Good Clinical Practice (GCP): Consolidated Guidance and the appropriate regulatory requirement(s). The investigators will be thoroughly familiar with the appropriate use of the treatment procedure as described in the protocol. Essential clinical documents will be maintained to demonstrate the validity of the study and the integrity of the data collected. Master files should be established at the beginning of the study, maintained for the duration of the trial and retained according to the appropriate regulations.

16 Ethical Considerations

The study will be conducted in accordance with ethical principles founded in the Declaration of Helsinki. The IRB/IEC will review all appropriate study documentation in order to safeguard the rights, safety and well-being of the patients. The study will only be conducted at sites where the IRB/IEC approval has been obtained. The protocol, informed consent, advertisements (if applicable), written information given to the patients, safety updates, annual progress reports, and any revisions to these documents will be provided to the IRB/IEC by the investigator.

17 Patient Information and Informed Consent

After the study has been fully explained, written informed consent will be obtained from either the patient or his/her guardian or legal representative prior to any study procedures. The method of obtaining and documenting the informed consent and the contents of the consent will comply with ICH-GCP and all applicable regulatory requirement(s).

18 Patient Confidentiality

In order to maintain patient privacy, all CRFs, study reports and communications will identify the patient by initials and the assigned patient number. The Investigator will grant monitor(s) and auditor(s) from BioSphere Medical or its designee and regulatory authority (ies) access to the patients' original medical records for verification of data gathered on the CRFs and to audit the data collection process. The patient's confidentiality will be maintained and will not be made publicly available to the extent permitted by the applicable laws and regulations.

19 Protocol Compliance

The Investigators will conduct the trial in compliance with the protocol provided by BioSphere Medical, and given approval/favorable opinion by the IRB/IEC and the appropriate regulatory authority(ies), if required. Modifications to the protocol should not be made without agreement of the investigator and BioSphere Medical. Changes to the protocol potentially affecting safety or

efficacy will require written IRB/IEC approval/favorable opinion prior to implementation, except when the modification is needed to eliminate an immediate hazard(s) to patients. The IRB/IEC may provide, if applicable regulatory authorities permit, expedited review and approval/favorable opinion for minor change(s) in ongoing trials that have the approval/favorable opinion of the IRB/IEC. BioSphere Medical will submit all protocol modifications to the regulatory authority (ies) in accordance with the governing regulations.

A record of patients screened, but not entered into the study, is to be maintained.

When immediate deviation from the protocol is required to eliminate an immediate hazard(s) to the patient, the investigator will contact BioSphere Medical or designee, if circumstances permit, to discuss the planned course of action and the action will be fully documented in the case report form and source documentation.

20 Monitoring, Verification of Data, Audit and Inspection

A BioSphere Medical monitor, or designee, will visit each center periodically to monitor the progress of the clinical trial and review CRFs and original source documents with the study personnel, to verify accuracy of data recording. Periodically some/all of the facilities used in the trial (e.g., laboratory) may be reviewed or inspected by the IRB and/or regulatory authorities.

The Investigator will ensure that the trial participants are aware of and consent that personal information may be reviewed during the data verification process as part of the monitoring/auditing by properly authorized agents of BioSphere Medical or subject to inspection by regulatory authorities. In addition, participation and personal information is treated as strictly confidential to the extent the applicable law permits and not publicly available. The audit or inspection may include, for example, a review of all source documents, drug records, original clinical medical notes, some or all of the facilities used in the trial.

21 Data Recording and Retention of Study Data

In compliance with Good Clinical Practice (GCP), the medical records/medical notes, etc. should be clearly marked and permit easy identification of participation by an individual in the specified clinical trial. The Investigator must record all data with respect to protocol procedures, drug administration, laboratory data, safety data and efficacy ratings on the BioSphere Medical CRFs.

If the Investigator relocates or retires, or otherwise withdraws his/her responsibility for maintenance and retention, BioSphere Medical must be notified (in writing) so that adequate provision can be made with regard to the trial documents.

Trial documents should be retained until at least two years after the last approval of a marketing application in an ICH region and until there are no pending or planned marketing applications in an ICH region by BioSphere Medical. Documents should be retained for a longer period, however, if required by the applicable regulatory requirements or by an agreement with BioSphere Medical, who will inform the investigator, in writing, as to when these documents no longer need to be retained.

22 Confidentiality, Publication and Disclosure Policy

The Investigators understand that BioSphere Medical will use the information developed in the clinical study in connection with the development of the study treatment. This information may be

disclosed to other clinical investigators, the FDA, and other government agencies. All information disclosed to the Investigators by BioSphere Medical for the purpose of having the Investigators conduct the clinical trial described in this protocol or generated by the Investigators as results in the clinical trial shall be treated by the Investigators as strictly confidential. The Investigators shall not use such information other than for the purpose of conducting the clinical trial and may not disclose such information to others, except when such disclosure is to colleagues and/or employees who reasonably require the information to assist in carrying out the clinical trial and who are bound by like obligations of confidentiality. Notwithstanding, the Investigators may use or disclose to others any information which: (i) was known to the Investigators prior to the date of its disclosure, (ii) is now, or becomes in the future, publicly available; or (iii) is lawfully disclosed to the Investigators on a nonconfidential basis by a third party who is not obligated to BioSphere Medical or any other party to retain such information in confidence.

APPENDIX A

1. Study Flowchart: Unilobar Disease

[figure not shown]
2. Study Flowchart: Bilobar Disease

3. Schedule of Study Events

1. Study Flowchart: Patients with Unilobar Disease

2. Study Flowchart: Patients with Bilobar Disease

3. Schedule of Procedures						
	Screening (within 4 weeks +/- 1 week of first TACE)	TACE Treatment Period ¹			Post-final TACE Study Visit ²	Survival Follow- up ³
	Visit -1	Tx Visit 1	Tx Visit 2	Tx Visit 3	Visit 4	
Informed Consent	X					
Eligibility criteria assessment	X					
Demographics	X					
Baseline HCC Review ⁴	X					
Medical History	X					
Concurrent Medical Conditions	X					
Physical Examination ⁵	X				X	
Vital signs	X				X	
Serum Pregnancy test	X					
Hematology / Serum Chemistry ⁶	X	X	X	X	X	
Urinalysis	X	X	X	X	X	
Tumor Evaluations (MRI) ⁶	X	X	X	X		
Alpha-feto protein (AFP) ⁶	X	X	X	X	X	
12-lead ECG	X				X	
Cardiac Ejection Fraction ⁷	X		X		X	
Randomization ⁸						
Embolization procedures (TACE)		X	X	X		
Resource Utilization		X	X	X		
Adverse Events		From randomization to protocol defined follow- up period				
Concomitant Medications		X				
Protocol deviations/violations		X				
Survival status						X
Additional cancer treatments						X
Pharmacokinetic Sampling ⁹		X				

¹ First TACE Cycle must be begin within 4 weeks (± 1 week) of baseline MRI and labs. If the patient has bilobar disease, the embolization of the first lobe must be within 4 weeks (± 1 week) of baseline MRI and labs and the second lobe must undergo embolization within 4 weeks (± 1 week) of the first lobe.

A second TACE cycle is required for all patients, unless the investigator deems further treatment unsafe for the patient. The second TACE cycle must be within 8 weeks (± 2 weeks) of first TACE cycle. If the patient has bilobar disease, the first lobe of the second TACE cycle must undergo chemoembolization within 8 weeks (± 2 weeks) of the second lobe in the first TACE cycle, and the second lobe of the second TACE cycle must undergo chemoembolization within 4 weeks (± 1 week) of first lobe in the second TACE cycle.

A third TACE cycle will be done for patients with MRI results for the liver after the second TACE cycle that demonstrate less than complete necrosis, as interpreted by the Central Reviewers, according to mRECIST criteria. The third TACE cycle must be done within 8 weeks (± 2 weeks) of the second TACE cycle. If the patient has bilobar disease, the first lobe of the third TACE cycle must undergo chemoembolization within 8 weeks (± 2 weeks) of the second lobe of the second TACE cycle, and the second lobe of the third TACE cycle must undergo chemoembolization within 4 weeks (± 1 week) of the first lobe in the third TACE cycle.

² Post final TACE study visit must occur within 4 weeks (± 1 week) of the final study MRI.

³ Patients will be followed for survival for 2 years after the first TACE embolization. Survival contacts will be performed every 3 months.

⁴ Includes baseline disease status (Child Pugh, Unilobar/Bilobar status, ECOG), prior hepatic treatments, risk factor assessment, and assessment for relevant baseline medical conditions.

⁵ Physical exam for the Post final TACE visit must be within 4 weeks (± 1 week) of final study MRI.

⁶ MRIs and labs (including AFP) will be performed 4 weeks (± 1 week) after each TACE cycle. For patients with bilobar disease, MRI must be within 4 weeks (± 1 week) of the second lobe embolization.

⁷ Cardiac ejection fraction may also be assessed as clinically indicated to evaluate a cardiac adverse event.

⁸ Randomization will occur as close to the day of the scheduled First TACE procedure as possible, preferably on the same day.

⁹ A blood sample will be drawn for PK analysis between 6a and 8a the day after the first embolization of the first TACE Cycle, again 6-8 hours later for patients who have not been discharged at that time, and on the day of the first follow-up MRI.

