This is a phase 3, multicenter, randomized, controlled study designed to evaluate the safety and effectiveness of treating patients with localized, non resectable hepatocellular carcinoma with conventional transarterial chemoembolization (cTACE) or HepaSphere/QuadraSphere transarterial chemoembolization (hqTACE).

The study will consist of a screening period in which patient eligibility will be determined. Patients meeting the study entry criteria will be randomized on a 1:1 basis to receive either cTACE or hqTACE. A TACE cycle is defined as a single embolization for patients with unilobar disease and an embolization of each lobe for patients with bilobar disease. Patients will receive up to 3 TACE cycles. The first embolization will be done within 4 weeks of baseline imaging, and the second and third TACE cycles will take place 8 and 16 weeks after the first TACE cycle, respectively. MRIs will be done 4 weeks after each TACE cycle to determine tumor response and will be assessed by Central Reviewers.

The primary study endpoint will be overall survival. Study treatment will end after a maximum of 3 TACE cycles. Patient survival will be followed from date of first study TACE procedure until a date of death is obtained or the patient is lost to follow-up. Treatments for hepatocellular carcinoma after the study TACE treatments are complete will be documented during the survival period to the extent possible.

For cTACE, 75 mg/m^2 of doxorubicin (maximum dose of 150mg of doxorubicin per TACE cycle) mixed with ethiodized oil will be delivered into the hepatic artery via microcatheter, and then the artery will be occluded with particle PVA. For the hqTACE, the 75 mg/m^2 of doxorubicin (maximum dose of 150mg of doxorubicin per TACE cycle) will be loaded onto the HepaSphere/QuadraSphere Microspheres (through ionic bonding when the spheres are exposed to doxorubicin solubilized in normal saline) and delivered via microcatheter. No ethiodized oil is used with the microspheres. Dosage will be calculated and rounded up to the nearest 25 mg of doxorubicin. The occlusion endpoint will be stasis to the second or third branches. If stasis has not been reached when the target dosage of doxorubicin has been delivered, additional bland embolic (particle PVA for the cTACE arm and HepaSphere/QuadraSphere for the hqTACE arm) will be used to achieve a consistent endpoint.

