In an effort to assess the level of patient blinding, per FDA recommendation, patients will be asked the following question after they have completed their protocol specified embolizations: *“What treatment do you think you received?”* with response options of cTACE, hqTACE, or Unknown. This data is informative in nature and will not have any influence on the analyses of the study outcomes.

The study will be unblinded once all of the patients have received up to three study TACE cycles and follow up study procedures (protocol specified treatment phase of the investigation) and the database has been cleaned and locked. Unblinded survival data collection will continue until all patients have died or been lost to follow-up.

Treatment and Assessment

Study patients will be randomized to receive hqTACE or cTACE, with a target dose of $75\text{mg}/\text{m}^2$ of doxorubicin for each TACE cycle (maximum dose of 150mg of doxorubicin per TACE cycle). Up to a total of 3 TACE cycles will be administered to each patient within approximately a 6 month period from initial treatment, based on response as determined by Central Reviewers, using mRECIST. See Study Flow Charts, Appendix A.

Taking windows for second and third TACE cycles into account (8 weeks \pm 2 weeks from prior TACE cycle) and assessments (4 weeks \pm 1 week from last embolization in current cycle), and a 4 week (\pm 1 week) time between treatment of lobes of patients with bilobar disease, the assessment of objective response rate for patients with unilobar disease will be 15-25 weeks and 24-40 weeks for patients with bilobar HCC.

Patients whose response to treatment during the study makes them eligible for potentially curative therapies such as transplant, resection or percutaneous ablation will be offered those treatments, as appropriate in the decision of the treating physician. They will be discontinued from the treatment portion of the study and followed for survival per protocol.

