7.9 Survival follow -up

Patients will be followed from date of first embolization of the first cycle until a date of death is obtained or the patient is lost to follow up. Survival contacts will be attempted every 3 months after completion of final protocol-specified study visit. Contacts may be by visit, telephone, email, or written response, and may be obtained from the patient, medical records, or care givers/family members. Patients may undergo further treatment after the study-specified TACE treatments at the discretion of their physicians, including but not limited to transplant, resection, percutaneous ethanol injection (PEI), radiofrequency ablation (RFA), additional

embolizations, sorafenib or other treatments, including other investigational methods. Patients who have additional embolizations after the three protocol-defined TACE cycles must have the same type of embolization (cTACE or hqTACE) they received during the study. It would be unethical to deny these patients further treatment which might provide benefit, but any and all of the above could affect long term survival and be confounds in the analysis and interpretation of this study data. For this reason treatments and outcomes after the final study TACE will be documented, to the extent possible, during the survival follow-up period, but will not be considered safety or efficacy outcomes in this study, except time to untreatable progression (TTUP). Survival and TTUP will be the only outcomes evaluated after completion of the protocol specified treatment phase of the investigation.

7. Withdrawal of Patients

Patients will be informed that they have the right to withdraw from the study at any time for any reason, without prejudice to their medical care. The investigator also has the right to withdraw patients from the study for any of the following reasons:

- Adverse events, including cardiac ejection fraction <50%
- Progression to extrahepatic disease
- Refusal of treatment
- Patient request
- Inability to complete study procedures
- Lost to follow up
- Non compliance with study requirements

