11.2 Sample Size Calculations

The sample size calculation for the primary efficacy analysis of the comparison of median overall survival between the two groups is based on the assumption of a 16 month median survival in the cTACE group and a 24 month median survival in the hqTACE group. A sample size of 196 patients per treatment group will have 85% power to detect this difference in median survival (Hazard ratio= 1.500) based on a 2-sided Type I error rate of 5%. Assuming a 30% non-evaluable rate, a total of 255 patients will be enrolled and randomized into each treatment group.

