11.5 Efficacy Analysis

11.5.1 Median Overall Survival

The primary efficacy analysis of median overall survival will be performed on the ITT population when the last patient has completed two years of follow-up after their first study TACE procedure or 218 deaths have been observed in the two groups combined, whichever comes first. Patients will be followed for survival until death or loss to follow up. Overall survival time will be calculated in months from the date of the first study TACE embolization to the date of death or date last known to be alive for patients who are lost to follow up. Median overall survival time will be calculated for each treatment group using the Kaplan-Meier (product-limit) method and corresponding 95% confidence intervals will be generated. Treatment groups will be compared on median survival using a log-rank test.

One and two year survival rates and corresponding 95% confidence intervals will also be calculated for both treatment groups. Survival analyses will also be performed for the Evaluable population.

In order to assess the consistency of observed treatment effect across investigational sites, a data poolability analysis will be performed on the primary efficacy outcome of overall survival using the ITT population. Median overall survival data will be summarized by site, including Kaplan-Meier plots. In addition, a Cox proportional hazards model will be run including factors for treatment group, investigational site, and an interaction term for treatment group and investigational site. For purposes of this analysis, sites enrolling fewer than 10 patients may be pooled into a single site.

A multivariate analysis of the primary efficacy outcome of overall survival will be performed using a Cox proportional hazards model for the ITT population. This analysis will be considered supportive only. The model will include factors for site, as well as all variables included in the final adaptive randomization model. In addition, key baseline factors found to be significantly different between the two treatment groups at baseline will also be evaluated in the model.

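### A schedule footnote stops survival follow-up at 2 years, while Sections 5, 6, 7.9 and 11.5.1 continue it until death or loss to follow-up

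*Combined protocol and SAP*

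**What the plan says.** Footnote 3 is attached to the Survival Follow-up column of the Schedule of Procedures: "Patients will be followed for survival for 2 years after the first TACE embolization". It adds contacts every 3 months.

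Four sections of the protocol body say otherwise:

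- Section 5 (Study Design) follows survival from the first study TACE "until a date of death is obtained or the patient is lost to follow-up".
- Section 6 (Randomization and Blinding): "Unblinded survival data collection will continue until all patients have died or been lost to follow-up".
- Section 7.9 (Survival follow-up) follows patients from the first embolization "until a date of death is obtained or the patient is lost to follow up", with 3-monthly contacts.
- Section 11.5.1 (Median Overall Survival): "Patients will be followed for survival until death or loss to follow up".

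Section 11.5.1 also times the primary analysis for "when the last patient has completed two years of follow-up after their first study TACE procedure or 218 deaths have been observed", whichever comes first, and requires this summary: "Median overall survival time will be calculated for each treatment group using the Kaplan-Meier (product-limit) method and corresponding 95% confidence intervals will be generated". Section 11.2 assumes a 16-month median for cTACE and "a 24 month median survival in the hqTACE group".

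**The concern.** For a patient alive at month 24 the two rules cannot both be followed: one closes survival follow-up and four keep it open. The schedule is the natural page from which a site plans its contacts, and this column feeds the primary endpoint. Section 7.9 also names time to untreatable progression (TTUP) as an outcome still evaluated in this period, so an early stop would cut those data short too.

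The limit falls exactly on the assumed hqTACE median. If no patient is observed past month 24, the hqTACE Kaplan-Meier curve ends at the point where it is expected to cross 0.5, so the median that Section 11.5.1 requires, and especially its upper confidence limit, may not exist.

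**Working it through.** **Inputs.** From Section 11.2: medians 16 and 24 months, hazard ratio 1.5, two-sided 5%, 85% power, 196 per group, 255 per group enrolled (510 in total). From Section 11.5.1: 218 deaths. Assumed: exponential survival, uniform accrual over A months (not stated, so a range is shown), no loss unless noted, and every site following the footnote.

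**1. The plan's own figures.**
- Schoenfeld: 4 × (1.960 + 1.036)² / (ln 1.5)² = 218.4, against 218 stated. Power at 218 deaths is 84.9%.
- Freedman: (1.960 + 1.036)² × (2.5/0.5)² = 224.5 deaths.
- P(death by 24 months): cTACE 1 − 2^(−24/16) = 0.646; hqTACE 1 − 2^(−24/24) = 0.500; mean 0.573.
- 224.5 / 0.573 = 392, or 196 per group, as stated. With Schoenfeld's 218.4 deaths the result is 191 per group.

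**2. What a 24-month limit leaves out.**
- Alive at 24 months: 35% of cTACE, 50% of hqTACE, 43% overall.
- Deaths that can be recorded: 510 × 0.573 = 292.
- If 30% were lost by 24 months (an assumption; the plan's 30% is a non-evaluable rate, not a loss rate), the loss hazard is −ln(0.7)/24 per month and the recordable total is 252. Both totals exceed 218.

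**3. Timing of the 218th death (510 patients, no loss).** Expected deaths at calendar month T are 510 times the average, over entry times and the two arms, of P(death by T − entry), with follow-up cut at 24 months under the footnote.

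| Accrual (months) | No limit | With limit | Delay | Recorded under the limit when the true 218th death occurs |
|---|---|---|---|---|
| 12 | 21.8 | 21.8 | 0 | 218 |
| 24 | 28.5 | 28.8 | 0.3 | 215 |
| 36 | 35.6 | 37.1 | 1.6 | 206 |
| 60 | 48.9 | 55.0 | 6.1 | 188 |

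The 218th death comes before the two-year leg of the trigger (A + 24 months) in every row. With the 30% loss assumption the delays for 24, 36 and 60 months are 1.1, 2.7 and 6.5 months.

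**4. Whether the hqTACE median can be estimated.** With the limit, the curve reaches 0.5 only if its value at month 24 is 0.5 or lower. When the true value is 0.5, that happens in about half of trials. The standard error with 255 patients is √(0.25/255) = 0.031, so the 95% range of the estimate is 0.44 to 0.56. Simulated trials analysed at the 218th recorded death (true median 24 months, no loss) give:

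| Accrual (months) | Estimable, no limit | Estimable, with limit |
|---|---|---|
| 12 | 22–24% | 22–24% |
| 18 | 56% | about 47% |
| 24 | 82–85% | about 50% |
| 36 | >99% | about 50% |
| 60 | 100% | about 50% |

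The ranges are the spread between repeated simulations. With 12-month accrual no patient has been followed for 24 months when the 218th death occurs at month 21.8, so the limit cannot act.

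The upper 95% limit of the median (log-log limits assumed, because the plan names no method) is estimable in 2–3% of trials with the limit, against 10, 61 and 99% without it for 24, 36 and 60 months.

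**5. Sensitivity (no loss).**
- If half of the patients are cut off at 24 months, the median is estimable in 78, 98 and 100% of trials for 24, 36 and 60 months of accrual.
- With 36-month accrual and everyone cut off, true hqTACE medians of 20, 22, 26 and 28 months give 94, 78, 24 and 10%, against 100, 100, 98 and 94% without the limit.

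**The case against.** The plan's intent is fairly clear. Four sections agree, one of them devoted to survival follow-up, and a single footnote is the outlier. Nothing shows that any site would stop contacts against Section 7.9. The primary test is unaffected, so what remains is one arm's descriptive median and its interval. The figure of about half depends on a true median of exactly 24 months, on universal adherence to the footnote and on accrual of about 2 years or more. With 24-month accrual the upper confidence limit would be estimable in only 10% of trials even without the footnote, so most of that problem comes from the 218-death trigger. All of this stands, and it limits the weight of the point.

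Three arguments do not remove it. The two years in Section 11.5.1 is one leg of the analysis trigger, tied to the last patient, and the text then repeats follow-up until death or loss. The footnote states a duration, not a minimum. No clause gives the body text precedence.

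Two stronger readings are tempting. A reader might infer that the trial loses power; at the plan's medians it does not, because 292 deaths can be recorded and 218 are needed. A reader might also infer from the exact match of 196 per group with 24 months per patient that a 2-year limit was intended. The match is suggestive only: the documents state neither the accrual time nor the follow-up behind the calculation, and four sections would then be wrong.

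**Conclusion.** The inconsistency is real and should be corrected. Its consequences are modest and conditional. Wherever the footnote is followed, deaths after month 24 go unrecorded and TTUP data end early; 43% of patients are expected to be alive at that point.

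At the primary analysis, the log-rank test at 218 deaths keeps its 5% error and about 85% power. If accrual lasts about 2 years or longer, all sites follow the footnote and the true hqTACE median is 24 months, the chance of obtaining that median falls to about one half, and the trigger is delayed by 0.3 to 6 months without loss. With 12-month accrual there is no effect at the primary analysis, and with 18-month accrual it is small. It also shrinks if only some sites follow the footnote.

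That 218 deaths stay reachable rests on the plan's medians. At the same hazard ratio, medians of 24/36 months give 222 recordable deaths in 510 patients under the limit, and 28/42 months give 198.

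**What to change.** Reword footnote 3 to: *Patients will be followed for survival from the first TACE embolization until death or loss to follow-up. Survival contacts will be performed every 3 months.* Sections 5, 6, 7.9 and 11.5.1 stay as they are.

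The sponsor should also confirm that the sample size of 196 per group was not meant to define a 2-year limit, and state the accrual and follow-up assumed in Section 11.2. The correction should reach sites before the earliest patients pass 24 months, because deaths missed after contact stops may be hard to recover.

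The cost is one line of text, with no added patients and no contacts beyond those that Section 7.9 already requires. The downside is that sites which planned contacts from the schedule must continue them past 2 years.
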